1.0 Introduction

We will measure COVID-19 related preventative health behaviors, including COVID-19 vaccinations, in the Contra Costa County, CA Medicaid managed care population. Our goal is to test ways to increase COVID-19 vaccination uptake. Our hypothesis is that as a result of financial, cultural, or access issues, among other things, vaccinations and other preventative health behaviors are too low from a public health standpoint, meaning relative to virus exposure and the potential adverse consequences of infection in low-income and racial/ethnic minority populations. Furthermore, we hypothesize that small financial incentives and other low-cost behavioral nudges can be used to reduce disparities, increasing vaccination rates and other behaviors known to mitigate the spread of the virus.

2.0 Brief Overview of the Study Protocol

Approximately 10,000 adult subjects will be recruited from the Contra Costa Health Plan (CCHP) via baseline survey. Subjects who complete the baseline survey will be randomized to the following arms:

1. Control Arm (n=2,500)
2. Informational Arm: no information/emotional message vs. safety and effectiveness information vs. information on consequences of going unvaccinated, race and/or gender concordant or discordant [7,500]

Each of these arms will be interacted with a financial incentive of \$10 (N=2,500) or \$50 (N=2,500) and, separately with a convenient link to the county public vaccine appointment scheduling system highlighted for participants (N=5,000).

The above treatments are designed to test the role of the following on vaccine take-up:

- Financial incentives [N=5,000] vs. no financial incentives [N=5,000]
 - 2,500 will be randomized to a \$10 incentive and 2,500 to a \$50 incentive
- Convenient scheduling link highlighted [N=5,000] vs. not [N=5,000]
- Messaging [N=7,500] vs not [2,500]
 - Message type: emotion [N=2,500] vs. safety and effectiveness [N=2,500] vs. consequences of not vaccinating [N=2,500]
- Race concordant [N=2,500] vs. race discordant messenger [N=2,500]
- Gender concordant [N=2,500] vs. gender discordant messenger [N=2,500]

We will obtain survey data on preventative health behaviors, including mask-wearing, hand washing, and willingness to vaccinate. We will obtain EMR data on vaccine take-up.

3.0 Study Staff Responsibilities

[figure not shown]
Pilot PI [name] will have ultimate responsibility for the study's design and implementation. She will be supported by Other Significant Contributors [name] and [name]. [name] will develop all study materials, including this MOP. She will be

responsible for monitoring and reporting adverse events (AEs), serious adverse events (SAEs), and other issues per the terms of the relevant Data and Safety Monitoring Plan (DSMP). She will obtain informed consent and HIPAA authorization from all subjects; recruit and randomize subjects; receive EMR data from CCHS; following the procedures in this MOP and the IRB-approved protocol; and report any protocol deviations to the IRB and other relevant parties. She will be responsible for protecting subjects' rights on a daily basis. She will oversee all data management procedures and quality control procedures.

Collaborator [name] of Conta Costa Health System (CCHS) will facilitate subject contacts and sharing of EMR data. CCHS will provide data on eligible CCHP members and will be responsible for screening members for eligibility.

4.0 Study Flow Diagram

Figure 1: Study Flow Diagram

5.0 Recruitment and Retention

A random sample of eligible CCHP members will be invited to participate in the study via email, mail, and/or text. We aim to recruit 10,000 subjects and recruitment will continue until we have reached 10,000 baseline survey responses.

We will provide gift cards for baseline survey completion (\$5 or \$25, depending on survey take-up). In addition, respondents will be entered into a raffle for \$250 gift cards.

5.1 Screening and Eligibility Criteria

CCHS will provide a list of eligible members and will be responsible for eligibility screening. Pilot PI [name] will not be responsible for eligibility screening. See 5.3 for Eligibility Criteria.

5.2 Screening Log

As screening will not be performed by Pilot PI [name] or her academic study team, this group will not maintain a screening log. Collaborator [name] will maintain documentation of eligibility determinations.

5.3 Eligibility Criteria

Eligible subjects are adult CCHP members with no previous COVID-19 vaccination history and no contraindications to COVID-19 vaccination, as determined in CCHP medical staff.

6.0 Informed Consent

Informed consent will be obtained during the baseline survey to recruit subjects. The IRB-approved consent documents are attached as an appendix.

6.1 HIPAA Authorization

Personal health information (PHI) will be obtained in keeping with the Health Insurance Portability and Accountability Act (HIPAA). The IRB approved a partial HIPAA waiver for purposes of study participant recruitment. The study outcome, COVID-19 vaccination, is PHI. The IRB-approved HIPAA authorization form is attached as an appendix.

7.0 Study Intervention

Subjects in treatment arms will receive interventions:

- Financial incentives [N=5,000] vs. no financial incentives [N=5,000]
 - 2,500 will be randomized to a \$10 incentive and 2,500 to a \$50 incentive
- Convenient scheduling link highlighted [N=5,000] vs. not [N=5,000]
- Messaging [N=7,500] vs not [2,500]
 - Message type: emotion [N=2,500] vs. safety and effectiveness [N=2,500] vs. consequences of not vaccinating [N=2,500]
- Race concordant [N=2,500] vs. race discordant messenger [N=2,500]
- Gender concordant [N=2,500] vs. gender discordant messenger [N=2,500]

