8.0 Randomization

We will stratify our sample based on race/ethnicity and age-group. Randomization will be performed in the RedCAP system. In practice, the randomization will divide the sample into 60 possible conditions:

1. Control [N=625]
2. Control x \$10 financial [N=312.5]
3. Control x \$50 financial [N=312.5]

4. Control x link [N=625]
5. Control x \$10 financial x link [N=312.5]
6. Control x \$50 financial x link [N=312.5]
7. No information/Emotional (language concordant) [N=625]
8. No information/Emotional (language concordant) x \$10 financial [N=312.5]
9. No information/Emotional (language concordant) x \$50 financial [N=312.5]
10. No information/Emotional (language concordant) x link [N=625]
11. No information/Emotional (language concordant) x \$10 financial x link [N=312.5]
12. No information/Emotional (language concordant) x \$50 financial x link [N=312.5]
13. Safety and effectiveness (race concordant, male) [N=156.25]
14. Safety and effectiveness (race concordant, male) x \$10 financial incentive [N=78.125]
15. Safety and effectiveness (race concordant, male) x \$50 financial incentive [N=78.125]
16. Safety and effectiveness (race concordant, male) x link [N=156.25]
17. Safety and effectiveness (race concordant, male) x \$10 financial incentive [N=78.125]
18. Safety and effectiveness (race concordant, male) x \$50 financial incentive [N=78.125]
19. Safety and effectiveness (race concordant, female) [N=156.25]
20. Safety and effectiveness (race concordant, female) x \$10 financial incentive [N=78.125]
21. Safety and effectiveness (race concordant, female) x \$50 financial incentive [N=78.125]
22. Safety and effectiveness (race concordant, female) x link [N=156.25]
23. Safety and effectiveness (race concordant, female) x \$10 financial incentive x link [N=78.125]
24. Safety and effectiveness (race concordant, female) x \$50 financial incentive x link [N=78.125]
25. Safety and effectiveness (race discordant, male) [N=156.25]
26. Safety and effectiveness (race discordant, male) x \$10 financial incentive [N=78.125]
27. Safety and effectiveness (race discordant, male) x \$50 financial incentive [N=78.125]
28. Safety and effectiveness (race discordant, male) x link [N=156.25]
29. Safety and effectiveness (race discordant, male) x financial incentive x link [N=78.125]
30. Safety and effectiveness (race discordant, male) x financial incentive x link [N=78.125]
31. Safety and effectiveness (race discordant, female) [N=156.25]

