32. Safety and effectiveness (race discordant, female) x \$10 financial incentive [N=78.125]

33. Safety and effectiveness (race discordant, female) x \$50 financial incentive [N=78.125]
34. Safety and effectiveness (race discordant, female) x link [N=156.25]
35. Safety and effectiveness (race discordant, female) x \$10 financial incentive x link [N=78.125]
36. Safety and effectiveness (race discordant, female) x \$50 financial incentive x link [N=78.125]
37. Consequences of going unvaccinated (race concordant, male) [N=156.25]
38. Consequences of going unvaccinated (race concordant, male) x \$10 financial incentive [N=78.125]
39. Consequences of going unvaccinated (race concordant, male) x \$50 financial incentive [N=78.125]
40. Consequences of going unvaccinated (race concordant, male) x link [N=156.25]
41. Consequences of going unvaccinated (race concordant, male) x \$10 financial incentive x link [N=78.125]
42. Consequences of going unvaccinated (race concordant, male) x \$50 financial incentive x link [N=78.125]
43. Consequences of going unvaccinated (race concordant, female) [N=156.25]
44. Consequences of going unvaccinated (race concordant, female) x \$10 financial incentive [N=78.125]
45. Consequences of going unvaccinated (race concordant, female) x \$50 financial incentive [N=78.125]
46. Consequences of going unvaccinated (race concordant, female) x link [N=156.25]
47. Consequences of going unvaccinated (race concordant, female) x \$10 financial incentive x link [N=78.125]
48. Consequences of going unvaccinated (race concordant, female) x \$50 financial incentive x link [N=78.125]
49. Consequences of going unvaccinated (race discordant, male) [N=156.25]
50. Consequences of going unvaccinated (race discordant, male) x \$10 financial incentive [N=78.125]
51. Consequences of going unvaccinated (race discordant, male) x \$50 financial incentive [N=78.125]
52. Consequences of going unvaccinated (race discordant, male) x link [N=156.25]
53. Consequences of going unvaccinated (race discordant, male) x \$10 financial incentive x link [N=78.125]
54. Consequences of going unvaccinated (race discordant, male) x \$50 financial incentive x link [N=78.125]
55. Consequences of going unvaccinated (race discordant, female) [N=156.25]
56. Consequences of going unvaccinated (race discordant, female) x \$10 financial incentive [N=78.125]
57. Consequences of going unvaccinated (race discordant, female) x \$50 financial incentive [N=78.125]

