58. Consequences of going unvaccinated (race discordant, male) x link [N=156.25]
59. Consequences of going unvaccinated (race discordant, male) x \$10 financial incentive x link [N=78.125]
60. Consequences of going unvaccinated (race discordant, male) x \$50 financial incentive x link [N=78.125]

Randomization assignments will be documented for future reference.

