messages aimed at clarifying the negative outcomes of not getting vaccinated are much more effective at changing intentions than messages that try to correct misperceptions about vaccine safety. Within the arm 3 and arm 4 message groups, we will further randomize participants to race/ethnicity concordant/discordant video messages and to gender concordant/discordant messages. This intervention builds on recent evidence that race-concordant health care providers increase health screening take-up (Alsan et al. 2019).

Each of these four arms will be interacted with a financial incentive of \$10 (N=2,500) or \$50 (N=2,500) and, separately with a convenient link to the county public vaccine appointment scheduling system highlighted for participants (N=5,000).

The above treatments are designed to test the role of the following on vaccine take-up:

- Financial incentives [N=5,000] vs. no financial incentives [N=5,000]
 - 2,500 will be randomized to a \$10 incentive and 2,500 to a \$50 incentive

- Convenient scheduling link highlighted [N=5,000] vs. not [N=5,000]
- Messaging [N=7,500] vs not [2,500]
 - Message type: emotion [N=2,500] vs. safety and effectiveness [N=2,500] vs. consequences of not vaccinating [N=2,500]
- Race concordant [N=2,500] vs. race discordant messenger [N=2,500]
- Gender concordant [N=2,500] vs. gender discordant messenger [N=2,500]

These financial incentives of \$10 or \$50 are in line with the prior literature. For example, Bronchetti, Huffman, and Magenheim (2015) paid college students \$30 for flu vaccinations in 2012. In addition, the \$50 incentive is in-line with 2 hours of time at the minimum wage plus transportation costs. These incentives will be paid for with funding from J-PAL. While financial incentives for vaccination have faced some criticism (Largent and Miller 2021), prior work suggests small incentives can be quite effective (Bronchetti, Huffman, and Magenheim 2015). Given the urgency of the issue, we think it is crucial to test the effectiveness of financial incentives against other potential tools to improve vaccine take-up. We will also examine study impacts for subpopulations of interest identified in our baseline survey (e.g., groups at a high risk for adverse health outcomes or young adults who have high potential to be super-spreaders of COVID-19).

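### The 60-condition randomization list does not match the stated factorial: six labels are duplicated, one messenger cell is missing, and messenger concordance is tied to the wrong total

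*Protocol*

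**What the plan says.** Protocol section 2.0 introduces its factor list with "The above treatments are designed to test the role of the following on vaccine take-up". The list, repeated in section 7.0 and in Appendix A (Amended Protocol, Methods), has these margins:

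- any financial incentive 5,000 against none 5,000, with $10 and $50 at 2,500 each;
- link highlighted 5,000 against not 5,000;
- message type: "Message type: emotion [N=2,500] vs. safety and effectiveness [N=2,500] vs. consequences of not vaccinating [N=2,500";
- race-concordant messenger 2,500 against discordant 2,500;
- "Gender concordant [N=2,500] vs. gender discordant messenger [N=2,500".

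Section 8.0 states that randomization in REDCap divides the sample into 60 conditions and prints them with cell sizes. Appendix A prints the same list. Two entries in the consequences arm read "52. Consequences of going unvaccinated (race discordant, male) x link [N=156.25" and "58. Consequences of going unvaccinated (race discordant, male) x link [N=156.25".

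On where the messenger varies, Appendix A (Methods) says: "Within the arm 3 and arm 4 message groups, we will further randomize participants to race/ethnicity concordant/discordant video messages", and adds gender in the same sentence. In that numbering arms 3 and 4 are safety and consequences. The emotion conditions (7–12) carry no messenger race or sex, for example "No information/Emotional (language concordant) [N=625". The section 2.0 overview of arms nevertheless ends with "information on consequences of going unvaccinated, race and/or gender concordant or discordant [7,500", which attaches concordance to all 7,500 messaged participants.

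**The concern.** The list in section 8.0 is the document's only cell-level specification of the allocation, and it disagrees with the margins in sections 2.0 and 7.0. Both copies carry the same faults, so neither corrects the other. If the list was programmed as printed, one planned cell would receive nobody, another would be doubled, two cells would lose the link, and two would have no defined payment. Factors designed to be balanced against each other would then be correlated.

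A smaller issue sits beside this. Message type and messenger appear as parallel items in the factor list, but the messenger is randomized in only two of the three message arms. Emotion against safety, or emotion against consequences, therefore compares content together with whatever messenger the emotion arm uses, which the text does not describe. Nothing in the factor list tells the reader so.

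**Working it through.** **Inputs** (section 8.0). Control and emotion: 625 per no-incentive cell and 312.5 per incentive cell. Safety and consequences: 156.25 per no-incentive cell and 78.125 per incentive cell, so each race × sex × link cell holds 156.25 + 2 × 78.125 = 312.5.

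**1. Reproducing the stated margins.** Read 58–60 as female messenger, 17–18 with the link, and 29–30 as $10 and $50.

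- Each of the four arms: 2,500. Total: 10,000.
- Messenger race: 2,500 and 2,500. Messenger sex: 8 × 312.5 = 2,500 male and 2,500 female.
- Link: 4 × 1,250 = 5,000.
- $10: 625 (control) + 625 (emotion) + 16 × 78.125 = 2,500. The $50 sum is the same.

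There are 60 distinct cells and every margin agrees. With messenger sex at 2,500 each, gender concordance is 2,500 against 2,500 whatever the share of women.

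**2. The list as printed.**

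| Conditions | Fault | Labels lost |
|---|---|---|
| 58–60 | repeat 52–54 (male), although they follow the female block 55–57 | 3 |
| 17–18 | link absent, so they repeat 14–15 | 2 |
| 29–30 | amount absent, so they are identical to each other | 1 |

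Distinct labels: 60 − 6 = 54.

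- Messenger sex, consequences arm: male 625 + 625 + 312.5 = 1,562.5 (62.5%), female 625 + 312.5 = 937.5. Safety arm: 1,250 and 1,250. Together: 2,812.5 male, 2,187.5 female.
- Race-discordant half of consequences: 937.5 male, 312.5 female.
- Link: 5,000 − 2 × 78.125 = 4,843.75 against 5,156.25.
- $10 and $50: 2,500 − 78.125 = 2,421.875 each, with 156.25 of unspecified amount.
- Gender-concordant N, with f the share of women (not given, so assumed, and taken as equal across cells): 2,812.5(1 − f) + 2,187.5f = 2,812.5 − 625f. At f = 40%, 50%, 60% and 70% this is 2,562.5, 2,500, 2,437.5 and 2,375. The stated 2,500 holds only at 50%.

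Arm totals and the race margin are unaffected.

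**3. Consequence for the contrasts if programmed as printed.**

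- Male messengers are 62.5% of consequences against 50% of safety, so the unadjusted comparison carries (0.625 − 0.5) = 0.125 of any messenger-sex effect. For assumed effects of 2, 4 or 6 points that is 0.25, 0.5 or 0.75 points.
- Race discordant against concordant carries the same fraction: 1,562.5/2,500 = 62.5% male against 50%.
- The link share in safety is (1,250 − 156.25)/2,500 = 43.75% against 50% in consequences.

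**4. Precision of safety against consequences,** at an assumed 20% take-up.

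- As intended: √(0.16 × 2/2,500) = 1.13 points.
- Least squares with additive terms for messenger race and sex, link and incentive, 58–60 as printed: 1.14.
- Comparing only within the seven shared race × sex × link cells (six at 312.5 against 312.5, one at 312.5 against 625, with 17–18 read as intended): √(0.16/(6 × 156.25 + 208.33)) = 1.18.
- Detectable difference at 80% power and two-sided 5% (2.80 × SE): 3.17 points as intended, 3.31 under the strictest comparison.

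**5. Where the messenger is randomized.** The messenger margins total 2,500 + 2,500 = 5,000, which is safety plus consequences and not 7,500. Conditions 13–60 all name messenger race and sex, and conditions 7–12 name neither. In the regular pattern, safety and consequences each have 625 in every race × sex messenger cell, so their messenger mix is matched. The emotion arm has no randomized messenger to match.

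**The case against.** The strongest reply on the list is that the intended cells can be recovered from the document. Conditions 58–60 follow a female block, the protocol states 60 conditions, and the regular pattern restores every margin. That stands, and it makes a label slip the likeliest explanation. It does not make the list safe to program from, and it does not show what was programmed. Even in the bad case the damage is limited: safety against consequences stays identified and its adjusted precision barely changes.

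On message type, a reader might infer that the protocol claims a content-only effect for the emotion message, or that emotion against information is a biased comparison. The documents support neither. No section claims that content is isolated. The nesting is disclosed in Appendix A and in the condition labels, and the only literature rationale about message content concerns consequences against safety. Emotion against either information arm is a valid randomized comparison of what participants receive. The text does not say who, if anyone, delivers the emotion message, and the design figures are not shown in the text at hand. What remains is the 7,500 in section 2.0 and the lack of a plain statement of what each message contrast compares.

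**Conclusion.** The list is wrong as printed, in both copies. Seven conditions carry faulty labels, 54 of 60 labels are distinct, one intended messenger-by-link cell is absent, and the stated link and incentive margins fail. The gender-concordance margin holds only if half the participants are women. This rests on summing the printed cells; the share of women, the take-up rate and the messenger-sex effects are assumptions used for illustration.

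It would go too far to conclude that participants were misallocated, since the document does not show the REDCap build. Whether correction can still precede programming is doubtful: the amendment of 06/01/2021 raises the survey payment because of low take-up, which suggests that recruitment had begun.

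The message-type point is secondary and a matter of wording. Safety against consequences is the contrast with a matched messenger mix. The messenger's contribution to the emotion contrasts has unknown size and sign and cannot be quantified from the documents.

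**What to change.** 1. In section 8.0 and in Appendix A, reconcile conditions 58–60, 17–18 and 29–30 with the intended factorial, so that 60 distinct conditions reproduce the margins in sections 2.0 and 7.0.
2. Check the allocation actually programmed in REDCap against that list. If it follows the printed labels, report the actual cell sizes and adjust the message, messenger, link and incentive contrasts for the other factors.
3. In section 2.0, attach messenger concordance to the 5,000 in the safety and consequences arms.
4. In the factor list (sections 2.0 and 7.0, and Appendix A), state that safety against consequences has a matched messenger mix, and that emotion against either information arm compares message packages. Stating the emotion arm's messenger and format would help.

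Cost: seven labels in two copies, a few sentences and one check of the programmed allocation, with no change to arms or sample size. Appendix A is the IRB-approved protocol, so edits there may need to go through the IRB. The sponsor gives up a content-only reading of the emotion contrasts.

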8.0 Randomization

We will stratify our sample based on race/ethnicity and age-group. Randomization will be performed in the RedCAP system. In practice, the randomization will divide the sample into 60 possible conditions:

1. Control [N=625]
2. Control x \$10 financial [N=312.5]
3. Control x \$50 financial [N=312.5]

4. Control x link [N=625]
5. Control x \$10 financial x link [N=312.5]
6. Control x \$50 financial x link [N=312.5]
7. No information/Emotional (language concordant) [N=625]
8. No information/Emotional (language concordant) x \$10 financial [N=312.5]
9. No information/Emotional (language concordant) x \$50 financial [N=312.5]
10. No information/Emotional (language concordant) x link [N=625]
11. No information/Emotional (language concordant) x \$10 financial x link [N=312.5]
12. No information/Emotional (language concordant) x \$50 financial x link [N=312.5]
13. Safety and effectiveness (race concordant, male) [N=156.25]
14. Safety and effectiveness (race concordant, male) x \$10 financial incentive [N=78.125]
15. Safety and effectiveness (race concordant, male) x \$50 financial incentive [N=78.125]
16. Safety and effectiveness (race concordant, male) x link [N=156.25]
17. Safety and effectiveness (race concordant, male) x \$10 financial incentive [N=78.125]
18. Safety and effectiveness (race concordant, male) x \$50 financial incentive [N=78.125]
19. Safety and effectiveness (race concordant, female) [N=156.25]
20. Safety and effectiveness (race concordant, female) x \$10 financial incentive [N=78.125]
21. Safety and effectiveness (race concordant, female) x \$50 financial incentive [N=78.125]
22. Safety and effectiveness (race concordant, female) x link [N=156.25]
23. Safety and effectiveness (race concordant, female) x \$10 financial incentive x link [N=78.125]
24. Safety and effectiveness (race concordant, female) x \$50 financial incentive x link [N=78.125]
25. Safety and effectiveness (race discordant, male) [N=156.25]
26. Safety and effectiveness (race discordant, male) x \$10 financial incentive [N=78.125]
27. Safety and effectiveness (race discordant, male) x \$50 financial incentive [N=78.125]
28. Safety and effectiveness (race discordant, male) x link [N=156.25]
29. Safety and effectiveness (race discordant, male) x financial incentive x link [N=78.125]
30. Safety and effectiveness (race discordant, male) x financial incentive x link [N=78.125]
31. Safety and effectiveness (race discordant, female) [N=156.25]
32. Safety and effectiveness (race discordant, female) x \$10 financial incentive [N=78.125]

33. Safety and effectiveness (race discordant, female) x \$50 financial incentive [N=78.125]
34. Safety and effectiveness (race discordant, female) x link [N=156.25]
35. Safety and effectiveness (race discordant, female) x \$10 financial incentive x link [N=78.125]
36. Safety and effectiveness (race discordant, female) x \$50 financial incentive x link [N=78.125]
37. Consequences of going unvaccinated (race concordant, male) [N=156.25]
38. Consequences of going unvaccinated (race concordant, male) x \$10 financial incentive [N=78.125]
39. Consequences of going unvaccinated (race concordant, male) x \$50 financial incentive [N=78.125]
40. Consequences of going unvaccinated (race concordant, male) x link [N=156.25]
41. Consequences of going unvaccinated (race concordant, male) x \$10 financial incentive x link [N=78.125]
42. Consequences of going unvaccinated (race concordant, male) x \$50 financial incentive x link [N=78.125]
43. Consequences of going unvaccinated (race concordant, female) [N=156.25]
44. Consequences of going unvaccinated (race concordant, female) x \$10 financial incentive [N=78.125]
45. Consequences of going unvaccinated (race concordant, female) x \$50 financial incentive [N=78.125]
46. Consequences of going unvaccinated (race concordant, female) x link [N=156.25]
47. Consequences of going unvaccinated (race concordant, female) x \$10 financial incentive x link [N=78.125]
48. Consequences of going unvaccinated (race concordant, female) x \$50 financial incentive x link [N=78.125]
49. Consequences of going unvaccinated (race discordant, male) [N=156.25]
50. Consequences of going unvaccinated (race discordant, male) x \$10 financial incentive [N=78.125]
51. Consequences of going unvaccinated (race discordant, male) x \$50 financial incentive [N=78.125]
52. Consequences of going unvaccinated (race discordant, male) x link [N=156.25]
53. Consequences of going unvaccinated (race discordant, male) x \$10 financial incentive x link [N=78.125]
54. Consequences of going unvaccinated (race discordant, male) x \$50 financial incentive x link [N=78.125]
55. Consequences of going unvaccinated (race discordant, female) [N=156.25]
56. Consequences of going unvaccinated (race discordant, female) x \$10 financial incentive [N=78.125]
57. Consequences of going unvaccinated (race discordant, female) x \$50 financial incentive [N=78.125]

58. Consequences of going unvaccinated (race discordant, male) x link [N=156.25]
59. Consequences of going unvaccinated (race discordant, male) x \$10 financial incentive x link [N=78.125]
60. Consequences of going unvaccinated (race discordant, male) x \$50 financial incentive x link [N=78.125]

Randomization assignments will be documented for future reference.

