29. Safety and effectiveness (race discordant, male) x financial incentive x link [N=78.125]
30. Safety and effectiveness (race discordant, male) x financial incentive x link [N=78.125]
31. Safety and effectiveness (race discordant, female) [N=156.25]
32. Safety and effectiveness (race discordant, female) x \$10 financial incentive [N=78.125]
33. Safety and effectiveness (race discordant, female) x \$50 financial incentive [N=78.125]
34. Safety and effectiveness (race discordant, female) x link [N=156.25]
35. Safety and effectiveness (race discordant, female) x \$10 financial incentive x link [N=78.125]
36. Safety and effectiveness (race discordant, female) x \$50 financial incentive x link [N=78.125]
37. Consequences of going unvaccinated (race concordant, male) [N=156.25]
38. Consequences of going unvaccinated (race concordant, male) x \$10 financial incentive [N=78.125]
39. Consequences of going unvaccinated (race concordant, male) x \$50 financial incentive [N=78.125]
40. Consequences of going unvaccinated (race concordant, male) x link [N=156.25]
41. Consequences of going unvaccinated (race concordant, male) x \$10 financial incentive x link [N=78.125]

42. Consequences of going unvaccinated (race concordant, male) x \$50 financial incentive x link [N=78.125]
43. Consequences of going unvaccinated (race concordant, female) [N=156.25]
44. Consequences of going unvaccinated (race concordant, female) x \$10 financial incentive [N=78.125]
45. Consequences of going unvaccinated (race concordant, female) x \$50 financial incentive [N=78.125]
46. Consequences of going unvaccinated (race concordant, female) x link [N=156.25]
47. Consequences of going unvaccinated (race concordant, female) x \$10 financial incentive x link [N=78.125]
48. Consequences of going unvaccinated (race concordant, female) x \$50 financial incentive x link [N=78.125]
49. Consequences of going unvaccinated (race discordant, male) [N=156.25]
50. Consequences of going unvaccinated (race discordant, male) x \$10 financial incentive [N=78.125]
51. Consequences of going unvaccinated (race discordant, male) x \$50 financial incentive [N=78.125]
52. Consequences of going unvaccinated (race discordant, male) x link [N=156.25]
53. Consequences of going unvaccinated (race discordant, male) x \$10 financial incentive x link [N=78.125]
54. Consequences of going unvaccinated (race discordant, male) x \$50 financial incentive x link [N=78.125]

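### The printed list of 60 randomization conditions contains only 55 distinct ones, and its link totals do not match the stated 5,000 versus 5,000

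*Protocol*

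**What the plan says.** Section 8.0 (Randomization) states: "In practice, the randomization will divide the sample into 60 possible conditions". A numbered list of 60 lines follows, each with a target N. Appendix A (Amended Protocol, April 2021, Randomization) repeats the list.

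The design is also stated in words and as totals:

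- Section 2.0 and the Methods text of Appendix A cross every arm with the incentive (none, USD 10, USD 50) and, separately, with the scheduling link.
- Section 7.0 gives the link total: "Convenient scheduling link highlighted [N=5,000] vs. not [N=5,000". It gives 5,000 with an incentive (2,500 at each amount) and 5,000 without, and for race: "Race concordant [N=2,500] vs. race discordant messenger [N=2,500".
- The Methods text of Appendix A says that within the two information arms "we will further randomize participants to race/ethnicity concordant/discordant video messages and to gender concordant/discordant messages".

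The lines at issue in the list are:

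- Lines 17-18, in the safety, race-concordant, male block, beginning "17. Safety and effectiveness (race concordant, male) x" and continuing with the incentive amount but no link.
- Lines 29-30, which share one label: "29. Safety and effectiveness (race discordant, male) x financial incentive x link [N=78.125". Appendix A has the same omission: "30. Safety and effectiveness (race discordant, male) x financial incentive x link [N=78.125".
- Lines 58-60, of which the first is "58. Consequences of going unvaccinated (race discordant, male) x link [N=156.25", although the block they close opens as female at line 55.

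**The concern.** This list is the only cell-level specification of the randomization in the document, and it directly follows the statement that REDCap performs the allocation. If someone built the allocation table from these labels, nobody would be allocated to the consequences message with a race-discordant female messenger and the link. Nobody would be allocated to the safety message with a race-concordant male messenger, an incentive and the link.

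The totals for message arm and race concordance would still come out at 2,500 per group, so a check of those totals alone would not reveal the fault. The groups behind them would differ in link exposure and messenger sex.

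Section 11.0 names giving a subject the wrong treatment as a protocol deviation. Assignments cannot be audited reliably against a list in which some cells are absent and two cannot be told apart.

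**Working it through.** **Inputs.** All come from the Section 8.0 list and the totals in Sections 2.0 and 7.0. Each block of six lines runs: no incentive, USD 10, USD 50, link, USD 10 with link, USD 50 with link. The control and emotional blocks have N = 625, 312.5, 312.5, 625, 312.5, 312.5. The eight messenger blocks have N = 156.25, 78.125, 78.125, 156.25, 78.125, 78.125.

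**Step 1: reproduce the stated figures from the full crossing.**

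- Message cells: control + emotional + 2 message types × 2 race × 2 messenger sex = 10.
- Conditions: 10 × 3 incentive levels × 2 link levels = 60.
- Total: 2 × 2,500 + 8 × 625 = 10,000.
- Link: 2 × 1,250 + 8 × 312.5 = 5,000.
- Messenger sex: 4 × 625 = 2,500 each.

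The stated 60 and 5,000/5,000 therefore follow from the crossing described in words.

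**Step 2: count the list as printed.** Lines 17-18 equal 14-15 (2 repeats) and lines 58-60 equal 52-54 (3 repeats), so 60 − 5 = 55 distinct conditions. If 29 and 30 are also taken literally as one label, the count is 54. With 29-30 read as the two amounts, five cells of the crossing are absent. Read literally, seven cells lack an exact label.

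**Step 3: size of the absent cells.**

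- Safety, race-concordant, male, incentive, link: 2 × 78.125 = 156.25.
- Consequences, race-discordant, female, link: 156.25 + 2 × 78.125 = 312.5.
- Sum: 468.75, and 468.75 / 5,000 = 9.4% of the messenger arms. The five repeated cells are doubled instead.

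**Step 4: totals as printed.**

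| Total | Stated or full crossing | As printed |
|---|---|---|
| Link / no link | 5,000 / 5,000 (stated) | 5,000 − 156.25 = 4,843.75 / 5,156.25 |
| USD 10, USD 50 | 2,500 each (stated) | 2,500 − 78.125 = 2,421.875 each, with 156.25 unlabelled |
| Male / female messenger | 2,500 / 2,500 (full crossing; not stated) | 2,500 + 312.5 = 2,812.5 / 2,187.5 |
| Race concordant / discordant | 2,500 / 2,500 (stated) | unchanged |
| Safety / consequences | 2,500 / 2,500 (stated) | unchanged |

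The link shortfall is 156.25 / 5,000 = 3.1% and comes only from lines 17-18. Lines 58-60 keep the link and move 312.5 subjects from female to male messenger.

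**Step 5: balance within contrasts, if the printed labels were used.**

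- Race concordant: link (1,250 − 156.25) / 2,500 = 43.75%; male messenger 1,250 / 2,500 = 50%.
- Race discordant: link 1,250 / 2,500 = 50%; male messenger (1,250 + 312.5) / 2,500 = 62.5%.
- Safety versus consequences gives the same figures: link 43.75% versus 50%, male messenger 50% versus 62.5%.

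**Step 6: gender concordance.** The documents do not give the share of men, p, so this step is illustrative. It assumes that p is the same in every cell.

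Concordant total = 2,812.5p + 2,187.5(1 − p) = 2,187.5 + 625p.

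| Assumed p | Concordant total | Men among concordant | Men among discordant |
|---|---|---|---|
| 30% | 2,375 | 35.5% | 25.0% |
| 50% | 2,500 | 56.25% | 43.75% |
| 60% | 2,562.5 | 65.9% | 53.8% |

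The stated total of 2,500 is met at 50% men. Even then, concordance is associated with the participant's own sex, by 10.5 to 12.5 percentage points over this range.

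**The case against.** The strongest reply is that this is an obvious labelling slip. The six-line pattern, the line numbers and every printed N agree with the full crossing. Lines 17-18 follow a link line, and lines 58-60 close a block that opens as female. Only one reading satisfies 60 conditions, 5,000 with the link and 2,500 at each incentive amount. On this view no N is wrong and the link mismatch arises only from reading two omissions as real allocations. Nothing shows that REDCap was programmed from these labels. The messenger-sex split contradicts no stated N, and the participant-sex figures rest on an assumed range.

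Most of this stands. The design is sound, the intended labels are recoverable, and Steps 5 and 6 describe a hypothetical. How the analysis would deal with any misallocation could also properly be left to the analysis plan.

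It does not remove the point. The error is not an artefact of text extraction or superseded wording, because Appendix A carries the same entries, and both the June 2021 amendment and the modifications log concern only the survey payment. No correct list exists elsewhere in the document. Allocation cells belong in the protocol or manual, and the document does not show whether the system was built from this list or from the crossing.

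**Conclusion.** The concern holds. As printed, the list has 55 distinct conditions (54 read literally) against the stated 60, and link totals of 4,843.75 and 5,156.25 against the stated 5,000 each. These contradictions rest on no assumption.

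The consequence is conditional. If REDCap follows the full crossing, only the text is wrong. If it follows the printed labels, five cells are empty and five doubled. The race-concordance and message-type contrasts would then each compare groups with 43.75% versus 50% link exposure and 50% versus 62.5% male messengers, while their group totals would still look correct. The link between gender concordance and participant sex depends on an assumed sex mix.

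This should be fixed: the error is certain, its effect can be checked, and correction is cheap.

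**What to change.** 1. Correct both lists (Section 8.0 and Appendix A) to agree with the stated crossing: add the link to lines 17-18, change lines 58-60 to female, and label lines 29-30 with the two stated incentive amounts in the order used by the other blocks.
2. Check the REDCap allocation table by cell as well as by total: link 5,000, each incentive amount 2,500, and the two messenger sexes equal within every combination of message, race concordance, link and incentive.
3. The amendment of 1 June 2021 raises the survey payment because of low take-up, so recruitment had apparently begun. Section 8.0 says that assignments are documented, so tabulate them by cell.
4. Only if anyone was allocated from the uncorrected list: report the actual cell sizes, and adjust the link, message-type, race-concordance and gender-concordance contrasts for the other randomized factors and participant sex.

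The cost is a corrected list, one check of the allocation table and one tabulation of existing records. No new data are needed.
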